The study will consist of 3 phases: a Screening Phase of up to 42 days in duration; a Treatment Phase (which includes a Safety Follow-up Visit occurring 30 days after the last dose of lerociclib); and a Post-Treatment Follow-up Phase (which includes a Survival Follow-up Phase) that will continue until participant death, loss of follow-up, withdrawal of consent, or the end of the overall study (whichever occurs first).

While receiving lerociclib, participants will undergo imaging assessments (via computed tomography [CT] of the chest/abdomen/pelvis with contrast or magnetic resonance imaging [MRI] with gadolinium) every 8 weeks for the first 12 months, then every 12 weeks thereafter. All participants will undergo a bone scan at baseline and annually thereafter (or as per the Investigator's standard of care).

If bone disease is identified, participants will require whole-body bone scans every 8 weeks for the first 12 months, then every 12 weeks thereafter.

Optional imaging modalities include a brain CT/MRI (if brain lesion[s] present at Screening), CT/MRI for any disease outside the chest/abdomen/pelvis (if lesion[s] identified at Screening), and/or skin color photography (if skin lesion[s] identified at Screening) every 8 weeks during the first 12 months, then every 12 weeks thereafter.

Number of Participants:

Approximately 100 participants will be enrolled and dosed in this study, with approximately 50 participants enrolled and dosed for each line of therapy (1L or 2L).

Intervention Groups and Duration:

Lerociclib is administered as a 150-mg tablet, to be taken orally twice daily (BID).

Based on current available data, lerociclib may be administered without regard to food; however, dosing under fed conditions appeared to improve gastrointestinal tolerability.

For this reason, as well as for consistency across the study population, participants in this study will be advised to take lerociclib after eating.

All participants (1L and 2L populations) will receive an AI (letrozole) or fulvestrant plus lerociclib 150 mg BID. All participants should be treated according to the best current practice guidelines and standard of care within each institution or country where the study is conducted.

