While receiving lerociclib, participants will undergo imaging assessments (via CT of the chest/abdomen/pelvis with contrast or MRI with gadolinium) every 8 weeks for the first 12 months, then every 12 weeks thereafter. All participants will undergo a bone scan at baseline and annually thereafter (or as per the Investigator's standard of care). If bone disease is identified, participants will require whole-body bone scans every 8 weeks for the first 12 months and then every 12 weeks thereafter.

Optional imaging modalities include a brain CT/MRI (if brain lesion[s] indicated at Screening), CT/MRI for any disease outside the chest/abdomen/pelvis (if lesion[s] identified at Screening), or skin color photography (if skin lesion[s] identified at Screening) every 8 weeks during the first 12 months, then every 12 weeks thereafter.

Participants will continue therapy until disease progression as determined by the Investigator per RECIST v 1.1, unacceptable toxicity, withdrawal of consent, start of a new anticancer treatment, discontinuation of the participant by the Investigator, or termination of the study by the Sponsor, whichever occurs first.

Following disease progression, participants will only be followed for survival, and will no longer require any scheduled assessments beyond that timepoint. Survival status will be assessed every 12 weeks regardless of the participant's reason for discontinuing study treatment.

Safety monitoring (AE/SAE monitoring, clinical laboratory tests, vital signs, 12-lead ECGs, physical examination), serial blood samples for PK, tumor biopsies, and bone scans will be performed at the timepoints specified in the study SoA ([Table 1](#)).

The study is anticipated to last for a total of approximately 48 months. This assumes 12 months to complete participant recruitment and a median PFS of 24 months, plus an additional 12 months for further monitoring.

An independent DSMB will be set up to periodically review and evaluate the accumulated study data for participant safety and for study conduct and progress, and to make recommendations to the Sponsor concerning the continuation of the study (as detailed in [Section 7.4](#)).

This study will be conducted in compliance with the protocol, GCP, and applicable regulatory and IRB/IEC requirements.

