5.2. Exclusion Criteria

Prospective participants are excluded from the study if **any** of the following criteria apply:

Medical Conditions

1. Has symptomatic visceral disease or any disease burden that makes the participant ineligible for endocrine therapy, per the Investigator's best judgment.
2. Has peritoneal carcinomatosis.
3. Has inflammatory breast cancer at Screening.
4. Has CNS involvement, **unless** participant is at least 4 weeks from prior therapy completion to starting study treatment, has stable CNS tumor at the time of Screening, and is not receiving steroids and/or enzyme-inducing anti-epileptic medications for brain metastases.
5. Has any clinically significant, uncontrolled heart disease and/or cardiac repolarization abnormality.
6. Has a history of prolonged QT syndrome or Torsades de Pointes.

Prior/Concomitant Therapy

7. Has received prior treatment with chemotherapy (**except** neoadjuvant/adjuvant chemotherapy), or with any CDK4/6 inhibitor.
8. Has received prior treatment with fulvestrant.
9. Use of systemic estrogens (eg, hormonal contraception, HRT).
10. Is currently receiving any of the following substances and cannot be discontinued 14 days prior to starting lerociclib:
 - Known strong or moderate CYP3A inducers or strong inhibitors of CYP3A

- Substances that have a narrow therapeutic window and are predominantly metabolized through CYP3A4/5
11. Has evidence of active bacterial infection, fungal infection, or viral infection (including SARS-CoV-2 or uncontrolled HIV, as noted below) which would preclude safe enrollment in the judgment of the Investigator.
- **Notes:**
 - The study SARS-CoV-2 requirements are determined by institutional standards (and local/country regulations, as applicable).
 - At Investigator discretion, any participant who tests positive and/or is symptomatic for SARS-CoV-2 during Screening may either be excluded from the study or delay enrollment until active infection has been excluded per institutional standards.
 - During the study, any SARS-CoV-2 testing is to be performed as clinically indicated for the individual participant. The Investigator must document the results of all tests performed. Any confirmed infection is to be recorded as an AE or, in the event that clinical manifestation warrants such, recorded and handled as an SAE as detailed in [Appendix 3](#).

Diagnostic Assessments

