8.1.1. Antitumor Activity Assessments

For tumor assessment, all sites of disease, including but not limited to the chest, abdomen, and pelvis, should be assessed radiologically by CT or MRI at Screening and every 8 weeks for the first 12 months, then every 12 weeks until the occurrence of disease progression ([Table 1](#)). A central imaging vendor will be used to collect and hold these images for possible future review by independent radiologists. Objective response data collected for the clinical study report will be based on Investigator assessment.

Scans (CT or MRI) obtained prior to informed consent will not need to be repeated if performed within 28 days prior to dosing. Radionuclide bone scans shall be performed at Screening for all participants and annually thereafter or as clinically indicated. All participants with a CR must have a radionuclide bone scan as part of confirmation of the CR. Additional scans may be obtained at the discretion of the Investigator, if clinically indicated.

Participants with bone-only disease will be followed with bone scans only at Screening and every 12 weeks on treatment.

If a participant shows a radiological response (CR or PR), a confirmatory radiological assessment will be performed at least 4 weeks after the response was first noted. Participants who have a confirmed CR will have a bone scan to confirm absence of bony metastases.

For all participants (1L or 2L populations), if they remain on therapy for 12 months following enrollment, the timing of CT or MRI scans should be lengthened to every 12 weeks.

The same method of assessment (CT or MRI) should be used to characterize tumors at Screening and at all follow-up assessments. If PET is used, it should also be accompanied by spiral CT or MRI.

Investigators should follow RECIST v1.1 Guidelines ([Eisenhauer 2009](#)) for tumor assessments and determination of overall response.

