8.1.1.1. Lesions: Identification and Follow-up

Measurable Lesions

Measurable tumor lesions are defined as tumor lesions with an LD (measured in at least 1 dimension) with a minimum size as follows ([Eisenhauer 2009](#)):

- 10 mm by CT or MRI (with a scan slice thickness of no greater than 5 mm)

Measurable lymph nodes must be ≥ 15 mm on the short axis by CT or MRI (with a scan slice thickness of no greater than 5 mm); only the short axis is to be measured at baseline and follow-up.

Lytic bone lesions or mixed lytic-blastic lesions with a soft tissue component meeting the definition of measurability above can be considered measurable lesions.

Cystic lesions representing cystic metastases that meet the definition of measurability described above can be considered measurable lesions. If present, noncystic lesions should be selected as target lesions for this study.

A tumor lesion that has been previously irradiated may be considered measurable if unequivocal growth of the lesion has been demonstrated.

Target lesions: At baseline, up to 5 measurable tumor lesions/lymph nodes (with a maximum of 2 lesions per organ) should be identified as target lesions that will be followed to quantitate the status of disease during the study. Lesions with the LD, that are representative of all involved organs, and for which reproducible repeated measurements can be obtained should be selected as the target lesions.

At Screening and at each follow-up timepoint ([Table 1](#)), each target lesion should be measured and the overall tumor burden will be calculated as the sum of the diameters of the target lesions (LD for tumor lesions and short axis for lymph nodes) and documented in the eCRF. If a target lesion fragments into multiple smaller lesions, the LDs of all fragmented portions are added to the sum of the diameters. If multiple lesions coalesce, the LD of the coalesced lesion will be included in the sum of the diameters.

Nonmeasurable Lesions

Nonmeasurable lesions include tumor lesions with an LD < 10 mm, lymph nodes with ≥ 10 to < 15 mm short axis, or nonmeasurable lesions such as leptomeningeal disease, ascites, pleural or pericardial effusion, inflammatory breast disease, lymphangitic involvement of skin or lung, or abdominal masses/abdominal organomegaly identified by physical exam that is not measurable by CT scan or MRI ([Eisenhauer 2009](#)).

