Nontarget lesions: All other lesions (or sites of disease) identified at baseline should be identified as nontarget lesions and recorded in the eCRF. Measurements of these lesions are not required, but the presence, absence, or unequivocal progression of each nontarget lesion should be recorded in the eCRF at each follow-up timepoint. Multiple nontarget lesions in the same organ may be noted as a single item on the eCRF.

New Lesions

Any new lesions should be identified and recorded at each follow-up assessment, as these are markers of disease progression. As defined in the RECIST v1.1 Guidelines ([Eisenhauer 2009](#)), new lesions include the following:

- A lesion in an anatomical location that was not scanned at baseline
- Equivocal new lesion of small size that with continued therapy and follow-up is found to progress and represent new disease (progression should be considered as of the date of the initial scan)
- Negative PET with FDG-PET at baseline, but has a positive FDG-PET at follow-up

No FDG-PET at baseline and a positive FDG-PET at follow-up that corresponds to a new site of disease as confirmed by CT (date of disease progression should be the date of the initial abnormal FDG-PET scan).

The need to initiate or increase the dose of a bisphosphonate and/or denosumab during the study **will be considered as indicative of clinical disease progression** leading to the discontinuation of participant from the active treatment phase **unless** disease progression can be completely ruled out and the exact reason for the use of these therapies is clearly documented in the participant's source documentation. All such cases must be first discussed with the Medical Monitor.

Note: Findings attributable to differences in scanning technique or a change in type of imaging (CT versus MRI) and findings representing something other than tumor (eg, healing or flare of existing bone lesions, necrosis of a liver lesion) should not be considered new lesions.

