Table 7: Evaluation of Overall Response at Each Timepoint (Continued)

| Target Lesions | Nontarget Lesions | New Lesions | Overall Response |
|----------------|--------------------------|-------------|------------------|
| PR | Non-PD/not all evaluated | No | PR |
| SD | Non-PD/not all evaluated | No | SD |
| NE | Non-PD | No | NE |
| PD | Any | Yes or No | PD |
| Any | PD | Yes or No | PD |
| Any | Any | Yes | PD |

CR = complete response; NE = not evaluable; PD = progressive disease; PR = partial response; SD = stable disease.
Source: [Eisenhauer 2009](#)

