3 INVESTIGATIONAL PLAN

3.1 Overall Study Design and Plan

This is a multicenter, single-arm, open-label study to evaluate the safety and efficacy of lerociclib administered in combination with standard endocrine therapy in female or male participants with HR+/HER2- mBC.

The study population will consist of newly diagnosed, treatment-naïve participants with HR+/HER2- mBC (the 1L population) and participants with HR+/HER2- mBC who have already progressed on first-line endocrine therapy such as tamoxifen, anastrozole, or letrozole (the 2L population). All premenopausal or perimenopausal female participants, and all male participants, must be receiving goserelin for at least 28 days prior to entering the study and will remain on goserelin throughout the study, in accordance with the prescribing information and according to the study site's standard practice.

The study will consist of 3 phases: A Screening Phase of up to 42 days in duration; a Treatment Phase (which includes a Safety Follow-up Visit occurring 30 days after the last dose of lerociclib); and a Survival Follow-up Phase that will continue until participant death, loss of follow-up, withdrawal of consent, or the end of the overall study (whichever occurs first).

While receiving lerociclib, participants will undergo imaging assessments (via computed tomography [CT] of the chest/abdomen/pelvis with contrast or magnetic resonance imaging [MRI] with gadolinium) every 8 weeks for the first 12 months, then every 12 weeks thereafter. All participants will undergo a bone scan at baseline and annually thereafter (or as per the Investigator's standard of

care). If bone disease is identified, participants will require whole-body bone scans every 8 weeks for the first 12 months and then every 12 weeks thereafter.

Optional imaging modalities include a brain CT/MRI (if brain lesion[s] indicated at Screening), CT/MRI for any disease outside the chest/abdomen/pelvis (if lesion[s] identified at Screening), or skin color photography (if skin lesion[s] identified at Screening) every 8 weeks during the first 12 months, then every 12 weeks thereafter.

Participants will continue therapy until disease progression as determined by Investigator per RECIST v 1.1, unacceptable toxicity, withdrawal of consent, start of a new anticancer treatment, discontinuation of the participant by Investigator, or termination of the study by the Sponsor, whichever occurs first.

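### On-treatment CT/MRI of brain and other out-of-field lesions known at Screening is optional in the design sections but expected in Protocol 8.1.1, so progression at a known nontarget site may be missed or found late

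*Protocol*

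**What the plan says.** **Design sections.** The Protocol synopsis has "Optional imaging modalities include a brain CT/MRI (if brain lesion[s] present at Screening), CT/MRI for any disease outside the chest/abdomen/pelvis", Protocol 4.1 has "Optional imaging modalities include a brain CT/MRI (if brain lesion[s] indicated at Screening), CT/MRI for any disease outside the chest/abdomen/pelvis", and SAP 3.1 has "Optional imaging modalities include a brain CT/MRI (if brain lesion[s] indicated at Screening". All three add skin photography to the list. Each item applies only if the lesion was found at Screening, and the sentence attaches the regular interval of 8 weeks in the first 12 months and 12 weeks afterwards.

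**Assessment sections.** Protocol 8.1.1 says "all sites of disease, including but not limited to the chest, abdomen, and pelvis, should be assessed radiologically by CT or MRI at Screening", and continues with the same 8-week and 12-week follow-up until progression. Under Protocol 8.1.1.1, at Screening and each follow-up timepoint "each target lesion should be measured and the overall tumor burden will be calculated as the sum of the diameters of the target lesions", and for the remaining lesions "the presence, absence, or unequivocal progression of each nontarget lesion should be recorded in the eCRF at each follow-up timepoint".

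**Schedule of activities.** The tumor-evaluation row gives the timing of RECIST assessment but no anatomical coverage. Bone scans have their own row and footnote; brain and other out-of-field imaging have neither.

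**Eligibility.** CNS involvement excludes a participant unless, among other conditions, that participant "has stable CNS tumor at the time of Screening". Participants with known brain lesions can therefore enter.

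**Response table.** Protocol Table 7 contains the row "SD | Non-PD/not all evaluated | No | SD" (target, nontarget, new lesions, overall response) and a matching row for PR.

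**The concern.** A site cannot both treat the scan of a known lesion as discretionary and follow every lesion at every timepoint. Protocol 4.1 sharpens the doubt: one paragraph earlier it makes whole-body bone scans obligatory once bone disease is found. A site could reasonably take the different word for brain and other out-of-field disease as intended.

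At stake is when progression is dated. If the first progression is in a known lesion that is not being imaged, the participant can go on being recorded as stable or responding until disease shows elsewhere, symptoms prompt a scan, or death occurs. PFS and DOR would then run long, and some participants could be credited with clinical benefit they did not have. The study has no control arm in which the same under-detection would occur, and imaging practice could differ between sites.

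**Working it through.** **1. Which lesions can be missed silently?** Reading Table 7 for a known out-of-field lesion that is not scanned:

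| Unscanned lesion | State of the rest | Overall response under Table 7 |
|---|---|---|
| Nontarget | Target SD, no new lesion | SD |
| Nontarget | Target PR, no new lesion | PR |
| Nontarget, recorded as not evaluated | Target CR, no new lesion | PR, so CR is already blocked |
| Target, so target response not evaluable | Nontarget not progressing, no new lesion | NE |

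The silent route is therefore mainly through nontarget lesions. A missing target lesion would usually surface as NE.

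**2. Does the SAP catch it?** SAP 4.10.2 derives the timepoint response from the lesion data entered and gives that derivation precedence over an investigator override in the primary evaluation. It has no rule for a baseline site that was not imaged. SAP 4.10.3.2 censors PFS at the last valid RECIST assessment but does not define valid. The SAP therefore neither accepts nor rejects such a timepoint explicitly.

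**3. How large could the effect be?** The documents give no figure for it, and no share of participants with such lesions, rate of skipped scans, or share of first progressions at those sites. The one relevant input is the planning median PFS of 24 months (Protocol 4.1), used there only for study duration. Everything else below is assumed, to show how far the answer moves. PFS is taken as exponential with λ = ln 2 / 24 = 0.0289 per month.

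*Delayed detection.* Let a share p of participants have their progression dated late, by an added exponential delay with a median of 12 months. With x = exp(−λt), S(t) = x + p·x − p·x². Setting S = 0.5 gives x = [(1 + p) − √((1 + p)² − 2p)] / (2p).

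- 10% with such lesions, 30% of these progressing there first, none scanned: p = 0.10 × 0.30 = 0.03, x = 0.4925, median 24.5 months (shift 0.5).
- 20%, 50%, none scanned: p = 0.20 × 0.50 = 0.10, x = 0.4751, median 25.8 months (shift 1.8).
- First case with only 30% of sites' scans skipped: p = 0.03 × 0.30 = 0.009, x = 0.4978, median 24.2 months (shift 0.2).

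*Never detected (upper bound for each pair of inputs).* Let a share f have such a lesion unscanned, and let a fraction s of their event hazard go undetected for good. Then S(t) = (1 − f)·exp(−λt) + f·exp(−λ(1 − s)t). For f = 10%, s = 50%, at t = 25.51: 0.4308 + 0.0692 = 0.500. Apparent medians in months:

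| f | s = 10% | s = 25% | s = 50% | s = 75% |
|---|---|---|---|---|
| 5% | 24.12 | 24.33 | 24.74 | 25.24 |
| 10% | 24.25 | 24.67 | 25.51 | 26.60 |
| 20% | 24.50 | 25.36 | 27.18 | 29.76 |
| 30% | 24.76 | 26.09 | 29.03 | 33.67 |

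The shift runs from 0.12 to 9.67 months. Apparent 12-month PFS runs from 70.8% to 77.0%, against 70.7%. If known sites are scanned as 8.1.1 says, the shift is zero.

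**4. Against the precision of the estimate.** With 50 participants per line, exponential PFS and no censoring, the standard error of the Kaplan-Meier median is √(0.25/50) / (0.5λ) = 0.0707 / 0.01444 = 4.9 months, or about ±9.6 months at 95%. Censoring would widen this.

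**The case against.** The best reply is that optional means only *additional, where applicable*: the sentence is conditional on a Screening lesion and carries a full schedule, and SAP 4.10.2 sends the reader to Protocol 8.1.1 for tumor assessment, not to 4.1. This reading is possible, and 8.1.1 itself says should. But the contrast with the obligatory bone scans points the other way, and the schedule of activities does not decide. An instruction that sites can read in two ways still needs correcting.

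A reader might go further and infer that PFS *is* overstated. The documents do not support that. The bias needs a site to skip the scan and the first progression to lie at the skipped site. Progression elsewhere, on an unscheduled scan or at death can still end PFS, and every cycle has a Day 1 physical examination. CNS entry is restricted and known bone disease has its own scans.

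A reader might also infer that the SAP accepts these timepoints as valid, or that it should reject them. It does not define the term. A rule rejecting them would contradict the PR and SD rows of Table 7, although SAP 4.13 declares no change to the protocol's methods. It could also do harm: SAP Table 2 censors a progression or death that follows two or more consecutive missed assessments, so two partly imaged visits reclassified as missing could remove a real event.

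It is also fair that the consequence is limited. The primary endpoint is the incidence of adverse events, and the shifts in step 3 are mostly small beside the sampling error in step 4. That bears on priority. It does not remove the conflict, since a systematic shift does not average out.

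**Conclusion.** The conflict stands: three design passages make imaging of known out-of-field lesions discretionary, while 8.1.1 and 8.1.1.1 expect it at every scheduled assessment. If a site uses the discretion, progression at a known nontarget lesion may be missed or found late, and PFS, with DOR and CBR, may be biased upward. The direction follows from the mechanism; the size cannot be estimated from the documents. The range in step 3 rests wholly on assumed shares and an exponential curve, and DOR and CBR were not calculated. No error rate, power or sample-size statement is touched, because all efficacy analyses are descriptive. The point merits correction mainly because it is cheap and the efficacy estimates have no internal comparator.

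**What to change.** 1. In the Protocol synopsis, Protocol 4.1 and SAP 3.1, replace the optional-imaging wording with a statement that CT/MRI of the brain or other out-of-field sites is performed at each scheduled tumor assessment when a lesion was present there at Screening, consistent with 8.1.1 and 8.1.1.1.
2. Add the same statement to the tumor-evaluation footnote of the schedule of activities, and to its copy in SAP Appendix 6.1.
3. State separately whether skin photography is required. Protocol 8.1.1 covers only CT and MRI, so it does not settle this.
4. Leave Table 7 and SAP Table 2 unchanged. Do not add a rule that such timepoints cannot support PR or SD, or are not valid.
5. If wanted, add a sensitivity analysis of PFS and response that flags timepoints at which a baseline-known site was not imaged.

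The cost is a wording change in a few places and, if chosen, one flag and one supplementary table. The practical downside is some additional scans at sites that would have treated them as optional, confined to participants with such lesions; they are CT/MRI scans that 8.1.1 already calls for.
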